9.4 Data management and quality control

For studies using eCRFs, Novartis personnel (or designated CRO) will review the data entered by investigational staff for completeness and accuracy. Electronic data queries stating the nature of the problem and requesting clarification will be created for discrepancies and missing values and sent to the investigational site via the EDC system. Designated investigator site staffs are required to respond promptly to queries and to make any necessary changes to the data.

Concomitant treatments and prior medications entered into the database will be coded using the WHO Drug Reference List, which employs the Anatomical Therapeutic Chemical classification system. Medical history/current medical conditions and adverse events will be coded using the Medical dictionary for regulatory activities terminology.

The occurrence of any protocol violations will be determined. After these actions have been completed and the data has been verified to be complete and accurate, the database will be declared locked. Authorization is required prior to making any database changes to locked data, by joint written agreement between the Global Head of Biostatistics and Data Management and the Global Head of Clinical Development.

For EDC studies, after database lock, the investigator will receive a CD-ROM or paper copies of the patient data for archiving at the investigational site.

10 Statistical methods and data analysis

Novartis or a designated Contract Research Organization will perform all analyses. Any data analysis carried out independently by the investigator should not be presented or published before the final analysis is completed. The data from all centers that participate will be combined in the analyses.

Final analyses will be performed when all patients have been followed for 30 days after they have either prematurely discontinued or been discontinued from the study after completing treatment as per protocol.

Data will be summarized with respect to demographic and baseline characteristics including FLT3 (ITD&TKD) and NPM1 mutation (when available), and safety and efficacy observations and measurements. Data may be summarized by different chemotherapy regimens (i.e. the “7+3” and the “5+2” induction regimens) and treatment phases (induction, consolidation and maintenance).

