10.3 Treatments (study treatment, concomitant therapies, compliance)

The safety set will be used for the analyses below. Categorical data will be summarized as frequencies and percentages. For continuous data, mean, standard deviation, median, 25th and 75th percentiles, minimum, and maximum will be presented.

Duration of midostaurin treatment exposure in days and cumulative dose and dose intensity will be summarized overall and by period and induction chemotherapy regimen by means of descriptive statistics using the safety set.

The number of patients with dose adjustments (reductions, interruption, or permanent discontinuation) and the reasons will be summarized for all patients and all dosing data will be listed.

Concomitant medications and significant non-drug therapies prior to and after the start of the study treatment will be listed and summarized according to the Anatomical Therapeutic Chemical (ATC) classification system, for all patients.

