10.5 Secondary objectives

The secondary objectives in this study are to assess the clinical efficacy of midostaurin in sequential combination with chemotherapy regimens in induction and consolidation and the clinical efficacy of midostaurin in maintenance phase (measured by CR/CRI rate).

Clinical efficacy rate is defined as the proportion of patients with complete remission (CR) or complete remission with incomplete hematologic recovery (CRI) as per local assessment, in induction, consolidation and maintenance. CR and CRI are defined according to the Revised Recommendations of the International Working Group for Diagnosis, Standardization of Response Criteria, Treatment Outcomes, and Reporting Standards for Therapeutic Trials in Acute Myeloid Leukemia, described in the ELN recommendations 2017 ([Dohner et al 2016](#)) (ENL).

Clinical efficacy rate will be calculated based on the FAS. Clinical efficacy rate and its 95% confidence interval will be presented by induction regimen and age category as described in [Section 10.5.3.1](#).

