10.5.3 Safety objectives

10.5.3.1 Analysis set and grouping for the analyses

For all safety analyses, the safety set will be used.

The overall observation period may be summarized into the following mutually exclusive periods:

1. **Pre-treatment period:** prior to first dose of midostaurin
2. **On-treatment period** (includes 3 mutually exclusive periods):
 - a. Induction period: From day of first dose of midostaurin to the day before start of consolidation period (i.e. end of induction phase plus any rest/recovery days)

- b. Consolidation period: From day of first dose of study treatment in consolidation phase to the day before start of maintenance (i.e. end of consolidation phase plus any rest/recovery days)
- c. Maintenance period: From day of first dose of midostaurin in the maintenance phase to the date of last dose of midostaurin + 30 days

It is noted that if a patient permanently discontinues study treatment during any of these periods, on-treatment is considered until the date of last dose of study treatment + 30 days (unless patient died before then, then it is till the death date)

3. **Post-treatment period:** from last date of study treatment + 31 days to end of study

Each period will contain all patients who entered that period (including withdrawal, drop-outs etc.).

Data may also be summarized by different chemotherapy regimens (i.e. the “7+3” and the “5+2” induction regimens) and by age category (i.e. patients younger than 60 years old and patients 60 years old or older).

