### **2.3 Subgroup analysis**

Safety and efficacy data will be reported for the following subgroups:

- Age [(i)  $\leq 60$  /  $> 60$  years old and/or (ii)  $\leq 60$  /  $> 60$  to  $\leq 70$  /  $> 70$  years old]
- Gender (female / male)
- Chemotherapy groups ('7+3' / '5+2')
- Type of induction drugs (Daunorubicin ( $< 60$  mg/m^2), daunorubicin ( $\geq 60$  mg/m^2) and Idarubicin)

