## 2.5.2 Study treatment and tolerability

### Study treatment

Duration of exposure (days), actual cumulative dose and actual dose intensity will be summarized by period and overall for each of the study drugs: midostaurin, daunorubicin and idarubicin for the safety set. Duration of exposure (days), actual cumulative dose and actual dose intensity will be summarized also by cycle. The number of patients with midostaurin dose changes, interruptions and permanent discontinuations will be presented by age category and overall, along with reasons for the dose change/interruption/permanent discontinuation.

Duration of midostaurin treatment exposure (days) will also be categorized and summarized by period and overall for the safety set using the following intervals:

- ≤ 20; >20; >40; >60; >120; >180; >240; >300; >360

Duration of study treatment exposure (days) will be summarized by period and overall for the safety set using the following intervals:

- ≤ 28; >28; >56; >84; >112; >196; >280; >364; >448; >532

Duration include the rest/recovery days between cycles and will be derived as the following:

Last intake of any study treatment component – first intake of any study treatment component +1

If there are more than 10 patients in each regimen exposure will be further summarized by regimen (“7+3” and “5+2”).

Data will be listed for all patients in the safety set.

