## **2.7 Analysis of the secondary objectives**

### **2.7.1 Secondary endpoints**

The secondary objectives in this study are to assess the clinical efficacy of midostaurin in combination with chemotherapy regimens in induction and consolidation and the clinical efficacy of midostaurin in maintenance phase.

Clinical efficacy rate will be presented for the FAS. All assessments before the last available on-treatment assessment will be included. Listings will include all data and will be based on the FAS. Records outside of on-treatment period will be flagged. For patients who discontinued prior to the first efficacy assessment, the response will be reported as ‘unknown’.

Clinical efficacy rate is defined as the proportion of patients with complete remission (CR) or complete remission with incomplete hematologic recovery (CRi) as per local review. The CR and CRi are defined by the national comprehensive cancer network (NCCN) guidelines version 1.2017 for AML.

Clinical efficacy rate and its 95% confidence interval will be presented by period (induction, consolidation and maintenance) and overall as described in [Section 2.1.1](#). The best overall response will be analyzed in each period and overall. If there are more than 10 patients in each regimen and age category, the clinical efficacy rate will be further summarized by regimen (“7+3” and “5+2”) and age category (e.g. <=60, >60 years and/or <= 60 / >60 to <=70 / > 70 years old) and by sex.

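### SAP 2.7.1 and 2.5.2 put a more-than-10-patients condition on the CR/CRi and exposure breakdowns that the protocol and SAP 2.3 do not contain, and the efficacy condition is ambiguous

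*SAP*

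**What the plan says.** **Efficacy.** Protocol 10.5 states that "Clinical efficacy rate and its 95% confidence interval will be presented by induction regimen and age category", with no minimum count. The sentence refers to protocol 10.5.3.1 for the groupings, and that section is permissive: "Data may also be summarized by different chemotherapy regimens", and likewise by age category. The opening text of protocol section 10 is also permissive on regimen: "Data may be summarized by different chemotherapy regimens".

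SAP 2.7.1 adds a condition: "If there are more than 10 patients in each regimen and age category, the clinical efficacy rate will be further summarized by regimen". The same sentence goes on to age category and sex. It gives the age bands only as examples, either two bands (60 or under, over 60) and/or three (60 or under, over 60 to 70, over 70). The SAP document history dates the three-band split to 09-Nov-2021, after database lock, and lists 2.7.1 among the sections affected.

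**Exposure.** Protocol 10.3 says that midostaurin exposure, cumulative dose and dose intensity "will be summarized overall and by period and induction chemotherapy regimen by means of descriptive statistics using the safety set". SAP 2.5.2 says "If there are more than 10 patients in each regimen exposure will be further summarized by regimen". This condition does not involve age.

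**Elsewhere in the SAP.** Section 2.3 has no count condition: "Safety and efficacy data will be reported for the following subgroups". Its list includes age, gender and the 7+3 and 5+2 chemotherapy groups. The AE summaries in 2.9.1 have no count condition. Section 4, on changes to protocol-specified analyses, says there are none.

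**The concern.** The primary objective names the 5+2 regimen, and protocol 2.2 presents the study as an extension of the pivotal trial to regimen variants and a wider population. The CR/CRi rate in the 5+2 group, and in older patients, is therefore among the results a reader will look for.

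The SAP sentence is all-or-nothing. If any category that counts towards the condition has 10 or fewer patients, the regimen, age and sex splits of the efficacy rate all fall away, including those for large groups such as 7+3 or either sex. A programmer who follows 2.7.1 would omit them. One who follows 2.3 would produce them. Because section 4 declares no change, a reader of the study report would not be told that the SAP had made a protocol output conditional.

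Protocol 2.3 describes 5+2 as a regimen used in advanced age, so a cell of younger 5+2 patients could well be small. If cells are what the condition counts, the choice between two and three age bands affects whether it is met, and the three-band option was added after lock.

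**Working it through.** **1. Figures in the plan.** Neither document gives a figure for this rule. The only sample-size figure is the 95% probability of seeing at least one patient with an AE of 1% incidence when N = 300. It reproduces, 1 − 0.99^300 = 0.951, and has no bearing here.

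**2. The texts side by side.**

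| Output | Protocol | SAP 2.3 | Specific SAP section |
|---|---|---|---|
| CR/CRi by regimen and age | 10.5: will be presented, no minimum (refers to 10.5.3.1: may) | will be reported, no minimum | 2.7.1: only if more than 10 in each regimen and age category |
| Exposure by regimen | 10.3: will be summarized, no minimum | not named separately | 2.5.2: only if more than 10 in each regimen |
| AEs | 10.5.3.2: will be summarized, no minimum | will be reported, no minimum | 2.9.1: no minimum |

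**3. Two readings of the 2.7.1 condition.**
- *Separate:* each regimen and each age band must exceed 10. It fails only if the 5+2 group (or, less plausibly, the 7+3 group) or an age band has 10 or fewer patients.
- *Crossed:* every regimen-by-age cell must exceed 10. One sparse 5+2 age cell is enough for it to fail.

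**4. Probability that the 5+2 group has 10 or fewer patients.** This applies to the exposure condition and to the regimen part of the separate reading. Inputs: N = 301 (SAP section 1) and an assumed 5+2 share p, since the documents give none. Formula: P(X ≤ 10) with X ~ Binomial(301, p).

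| Assumed share | Expected number | P(X ≤ 10) |
|---|---|---|
| 3% | 9.0 | 0.70 |
| 4% | 12.0 | 0.34 |
| 5% | 15.1 | 0.11 |
| 10% | 30.1 | about 0 |

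**5. Crossed reading.** This is the probability that at least one 5+2 age cell has 10 or fewer patients, from a multinomial with N = 301. The age mix within 5+2 is also assumed: for two bands from 50/50 to 10/90, for three bands from equal thirds to 10/40/50.

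| Assumed share | Two bands | Three bands |
|---|---|---|
| 5% | 0.98 to 1.00 | 1.00 |
| 10% | 0.21 to 1.00 | 0.93 to 1.00 |
| 20% | 0 to 0.96 | 0.03 to 0.96 |

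At a 10% share the 5+2 group as a whole is comfortably above 10. Whether the efficacy breakdown appears then depends on which reading and which banding are used.

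**6. Does precision change at the cut-off?** Exact (Clopper-Pearson) 95% intervals: 7/10 gives 34.8% to 93.3%, width 0.59; 7/11 gives 30.8% to 89.1%, width 0.58. There is no sharp change between 10 and 11 patients.

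**The case against.** A minimum count for displaying descriptive subgroups is common practice. The threshold is a fixed number written into the SAP, it depends on group size and not on outcome, and the document history records no entry that added it. Protocol 10.5 also points to a section that says the groupings may be used, so its commitment is softer than its own verb suggests. No hypothesis is tested, and listings will still hold all response data for the full analysis set and all exposure data for the safety set.

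These points stand as far as they go. They do not resolve the conflict. Protocol 10.3 carries no such cross-reference, SAP 2.3 is unconditional for efficacy, and section 4 reports no change. Listings do not replace a rate with its confidence interval.

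A reader might infer four stronger claims that the documents do not support.
- *That all 5+2 versus 7+3 results are suppressed.* The conditions cover the efficacy rate and exposure only. AE summaries have none, and 2.3 still commits to efficacy by chemotherapy group, so the SAP contradicts itself more than it settles on suppression.
- *That a sparse age cell removes exposure results.* The 2.5.2 condition has no age component.
- *That the efficacy condition is bound to fail.* The crossed reading is one of two, and neither the 5+2 share nor its age mix is given. Protocol 2.2 allows 5+2 for toxicity as well as age. SAP 2.1.8 also places every patient with under 7 days of cytarabine in the first induction cycle in the 5+2 group, which could add younger patients. With 10% on 5+2 and 40% of them aged 60 or under, the expected cell is 301 × 0.04 = 12.0 and P(10 or fewer) is 0.34.
- *That the rule was set after the counts were seen.* Only the three-band age split is dated after lock.

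**Conclusion.** The concern holds as an undeclared and ambiguous condition that conflicts with other text. SAP 2.7.1 and 2.5.2 make conditional what protocol 10.5, protocol 10.3 and SAP 2.3 state with no minimum count, and section 4 does not say so. Suppression of the efficacy breakdown is a possibility whose size depends on unstated quantities. If only the 5+2 group total matters, the risk is material at assumed shares up to about 5% and negligible at 10%. On the crossed reading it can remain high at 10% or more. The exposure condition carries only the first of these risks.

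This is more than missing detail. Followed literally, the rule can drop a protocol-specified efficacy result for the 5+2 extension, along with age and sex results that have no small-number problem of their own. It should be corrected. It does not touch the AE summaries that form the primary endpoint.

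**What to change.** - Delete the count condition in SAP 2.7.1 for the one-way breakdowns. Always present CR/CRi by regimen, by age category and by sex, with n/N and an exact 95% confidence interval.
- Delete the condition in SAP 2.5.2. Always present exposure by regimen with n and descriptive statistics; for very small groups give at least n, median, minimum and maximum.
- If a minimum count is wanted, apply it cell by cell to a regimen-by-age cross-table only, state which age banding it uses, and record it in SAP section 4 as a change from the protocol.
- Check that 2.3, 2.5.2 and 2.7.1 then agree.

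The cost is SAP wording and a few table rows with small denominators and wide intervals. No data collection changes.

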### **2.7.2 Statistical hypothesis, model, and method of analysis**

Not applicable.

### **2.7.3 Handling of missing values/censoring/discontinuations**

Not applicable.

## **2.8 Analysis of secondary efficacy objective(s)**

Not applicable.

## **2.9 Safety analyses**

The primary objective is to further assess the safety of midostaurin in induction, consolidation and maintenance therapy including the ‘7+3’ regimen, daunorubicin (60-90mg/m^2/day), the substitution of daunorubicin by idarubicin (12 mg/m^2/day) and cytarabine (100-200 mg/m^2/day) and also allowing the “5+2” reduced dose regimen.

Except for baseline values, safety summary tables will only include on-treatment assessments (up to 30 days after study treatment discontinuation) and will be based on the safety set. Listings will include all data and will be based on the safety set.

### **2.9.1 Adverse events (AEs)**

The AEs will be re-coded using the latest version of the medical dictionary for regulatory activities (MedDRA) at the time of the analysis.

AEs will be graded using the common toxicity criteria for adverse events (CTCAE) Version 4.03. AEs will be summarized by period and overall for the safety set. AEs tables will be provided by age category. AEs with different starts dates in different periods will be counted within each period. If a patient reported more than one AE with the same preferred term (PT), the AE with the greatest severity will be presented. If a patient reported more than one AE within the same primary system organ class (SOC), the patient will be counted only once with the greatest severity at the SOC level, where applicable. An AE with missing CTCAE grade will be included in the 'All grades' column of the summary tables.

In AE summaries, the primary SOC will be presented alphabetically and the PTs will be sorted within the primary SOC in descending frequency.

Summary tables will be provided for:

- Overview of AEs and age category
  - In-text table
- All AEs regardless of relationship to study treatment by primary system organ class (SOC), preferred term (PT) and maximum severity and age category
  - In-text table by SOC and maximum severity
  - In-text table by PT and maximum severity
- AEs suspected to be related to study treatment by SOC, PT and maximum severity and age category
  - In-text table by PT and maximum severity
- AEs leading to treatment discontinuation regardless of relationship to study treatment by SOC, PT and maximum severity and age category
  - In-text table by PT and maximum severity
- AEs leading to treatment reduction or interruption regardless of relationship to study treatment by SOC, PT and maximum severity and age category
  - In-text table by PT and maximum severity
- Serious AEs (SAEs) regardless of relationship to study treatment by SOC, PT and maximum severity and age category
  - In-text table by PT and maximum severity
- On-treatment deaths by SOC and PT and age category
  - In-text table by SOC and PT
  - All deaths by SOC, PT and age category
- \*Non-SAEs regardless of relationship to study treatment (threshold=5%) by SOC and PT
- \*On treatment deaths and SAEs by SOC and PT

\*(For the legal requirements of ClinicalTrials.gov and EudraCT, two required tables on <on-treatment/treatment emergent> AEs which are not SAEs with an incidence greater than 5% and on <on-treatment/treatment emergent> SAEs and SAE suspected to be related to study treatment will be provided by SOC and PT on the safety set.

If for a same patient, several consecutive AEs (irrespective of study treatment causality, seriousness and severity) occurred with the same SOC and PT:

- a single occurrence will be counted if there is  $\leq 1$  day gap between the end date of the preceding AE and the start date of the consecutive AE
- more than one occurrence will be counted if there is  $> 1$  day gap between the end date of the preceding AE and the start date of the consecutive AE

For occurrence, the presence of at least one SAE/SAE suspected to be related to study treatment/non SAE has to be checked in a block e.g., among AEs in a  $\leq 1$  day gap block, if at least one SAE is occurring, then one occurrence is calculated for that SAE.

The number of deaths resulting from SAEs suspected to be related to study treatment and SAEs irrespective of study treatment relationship will be provided by SOC and PT.

Listings will be provided for all AEs, SAEs and AEs leading to discontinuations (including those from the pre and post-treatment periods). Records outside of on-treatment period will be flagged.

#### **2.9.1.1 Adverse events of special interest / grouping of AEs**

The adverse events of special interest (AESI) are maintained and updated on a regular basis in the project case retrieval sheet (CRS) and the latest version at the time of the analyses will be used. The CRS to produce AESI outputs will be stated in listing 14.3.2-8.

A summary table for AESIs will be provided by period and overall for the safety set.

#### **2.9.2 Deaths**

See [Section 2.8.1](#). A listing will be provided of all deaths. Deaths outside of the on-treatment period will be flagged.

#### **2.9.3 Laboratory data**

Laboratory values are converted to the international system of units (SI). CTCAE Grade 0 will be assigned for all non-missing values not graded as 1 or higher. Grade 5 will not be used. For laboratory results where grades are not defined by CTCAE v4.03, results will be categorized as low/normal/high based on laboratory normal ranges.

The following summaries will be generated separately for key hematology and biochemistry by period and overall for the safety set:

- Shift tables by grade (or low/normal/high if grades not available) to compare baseline to the worst on-treatment value:
  - Hematology: Neutrophils (absolute) and platelets
  - Chemistry: Creatinine, total bilirubin, aspartate aminotransferase (AST), alanine aminotransferase (ALT) and alkaline phosphatase

Listing of all laboratory data (including urinalysis, coagulation, thyroid panel, pregnancy test etc.) will be provided with the corresponding CTCAE grades, if applicable, and the classifications relative to the laboratory normal ranges. Records outside of on-treatment period will be flagged.

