6.3.3 Dose modifications and management of toxicity during maintenance therapy

6.3.3.1 Hematologic toxicity

In the presence of grade 4 neutropenia during maintenance therapy, midostaurin must be held until ANC $\geq 1000/\mu\text{L}$. Once ANC $\geq 1000/\mu\text{L}$, then resume midostaurin at the previous dose. If neutropenia persists for more than two weeks, then discontinue midostaurin protocol.

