6.5.2 Treatment assignment

Patients who fulfill all entry criteria will receive midostaurin (investigational drug) on day 8 of the first induction cycle.

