7.1.2 Screening

Patients who are newly diagnosed with AML, have a known FLT3 ITD or TKD mutation and who have already started a “7+3” or “5+2” chemotherapy regimen in first induction will be consented and screened during the screening/baseline period (between C1D1 (chemotherapy already started) to C1D7) at least all the activities should be completed at Day 7 of the first chemotherapy (at Day -1). Re-screening is not allowed in this study.

The historical BMA result used to diagnose AML to the patients can be considered a part of inclusion criteria in the study.

If an historical BMA is available within 15 days before C1D1 of the first chemotherapy there is no need to repeat this assessment during the screening/baseline period.

If in case an historical BMA is not available within the 15 days before C1D1 of the first chemotherapy, a BMA should be performed during the screening/baseline period of the study.

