7.1.4.3 Maintenance phase

Patients who continue to achieve CR/CRI after (up to) four cycles of consolidation therapy will receive midostaurin maintenance therapy. Prior to initiation of midostaurin maintenance

therapy, all significant acute toxicity from consolidation therapy must have resolved to < grade 2.

For CR patients, midostaurin maintenance therapy will begin after hematologic recovery (ANC \geq 1 000/ μ L, platelet count \geq 100 000/ μ L) occurs and for CRi patients per investigator discretion and at least 3 days and no later than 28 calendar days after the last dose of consolidation midostaurin.

Each maintenance cycle is 28 days treatment. Subsequent cycles start on the day after the previous cycle is completed. In other words, subsequent cycles start 29 calendar days from the start of the previous cycle.

Patients who are unable to complete the cytarabine consolidation cycles because of toxicity or insufficient hematologic recovery may still be eligible for maintenance therapy. Discuss this situation in advance with the Novartis Study Team.

Refer to [Table 6-3](#) for maintenance treatment schedule.

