#### **2.1.2 Baseline**

Baseline is the result of an investigation describing the “true” uninfluenced state of the patient, defined as the period from the date of signing any informed consent document to the start date of midostaurin.

The last non-missing assessment, including unscheduled assessments on or before the first dose of midostaurin is defined as “baseline value” or “baseline assessment”. Assessments, specified to be collected post-dose on the first date of midostaurin are not considered for baseline.

Where electrocardiogram (ECG) replicates are provided, the average of the ECG parameters at that assessment will be used in the analyses.

If patients have no value as defined above, the baseline value will be missing.

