#### **2.1.5 Time windows**

Time windows for assessments are based on protocol specified windows, see protocol Table 7-1.

If more than one assessment is done within the same time window, the assessment performed closest to the target date will be used. For two assessments within a time window are equidistant from the target date then the earlier of the two assessments will be used. If there are multiple assessments for the same date, then the worst case will be used.

For unplanned visits, will be classified as follows:

Assessment	Target day of assessment	Time Interval
Baseline	Date when visit = IND C1D8 (or Day1)	Last date $\leq$ date of IND C1D8
INDC1	Date when visit = IND C1D8	Date of IND C1D8 - 7 $\leq$ date $<$ date of IND C2D1
INDC2	Date when visit = IND C2D8	Date of IND C2D1 $\leq$ date $<$ date of CON C1D1
CONC1	Date when visit = CON C1D8	Date of CON C1D1 $\leq$ date $<$ date of CON C2D1
CONC2	Date when visit = CON C2D8	Date of CON C2D1 $\leq$ date $<$ date of CON C3D1
CONC3	Date when visit = CON C3D8	Date of CON C3D1 $\leq$ date $<$ date of CON C4D1
CONC4	Date when visit = CON C4D8	Date of CON C4D1 $\leq$ date $<$ date of MAIN C1D1
MAINC1	Date when visit = MAIN C1D1	Date of MAIN C1D1 $\leq$ date $<$ date of MAIN C2D1

...	...	...
MAINC12	Date when visit = MAIN C12D1	Date of MAIN C12D1 <= date <= date of last non-zero dose +30
End Of Treatment	Date when visitnum =399	Date when visitnum in (399, 399.001,399.002,...)

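### The maintenance neutrophil and platelet shift tables use a baseline from first-induction chemotherapy, so they cannot separate new from persistent cytopenia

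*SAP*

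**What the plan says.** SAP 2.9.3 (Laboratory data) plans shift tables by CTCAE grade for absolute neutrophils, platelets and five chemistry parameters. They are produced for each treatment period and overall on the safety set, "to compare baseline to the worst on-treatment value".

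The baseline is fixed in SAP 2.1.2: "The last non-missing assessment, including unscheduled assessments on or before the first dose of midostaurin is defined as" the baseline value. The window table in SAP 2.1.5 has a single baseline row, aimed at induction C1D8. Neither document sets a new baseline for consolidation or maintenance.

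On timing, protocol 6.5.2 states that eligible patients "will receive midostaurin (investigational drug) on day 8 of the first induction cycle". Under protocol 7.1.2 they "will be consented and screened during the screening/baseline period", which runs from Day 1 to Day 7 of that cycle with chemotherapy already under way.

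On entry to maintenance, protocol 7.1.4.3 says that for patients in complete remission (CR) "midostaurin maintenance therapy will begin after hematologic recovery", defined as ANC of at least 1000/µL and platelets of at least 100,000/µL. For patients in CR with incomplete recovery (CRi), the start is left to the investigator.

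During maintenance, protocol 6.3.3.1 adds: "In the presence of grade 4 neutropenia during maintenance therapy, midostaurin must be held until ANC" is back to at least 1000/µL.

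**The concern.** A shift table is meant to show how a patient's grade changed over the period in its title. The maintenance table starts instead from a count taken in active leukemia, during or just after the first anthracycline and cytarabine course. Remission induction and up to four consolidation cycles lie between that count and the first maintenance dose. A change displayed for maintenance therefore mixes recovery that came before maintenance with whatever happened during it.

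This matters because maintenance is the only phase in which midostaurin is given without chemotherapy, and protocol 2.6 itself notes that causality is hard to judge when the drug is combined with chemotherapy. Protocol 10.5.3.3 marks laboratory abnormalities as not applicable, so the SAP 2.9.3 shift tables are the only aggregate laboratory summary that either document specifies. The rest is listings.

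**Working it through.** The plan gives no figure on this point. Its one design probability, a 95% chance of seeing at least one event of 1% incidence in 300 patients, reproduces (1 − 0.99^300 = 0.9510), but nothing below depends on it.

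**Step 1. Trace the definitions.** There is one baseline per patient (SAP 2.1.2, 2.1.5). It falls on or before Day 8 of induction cycle 1 (protocol 6.5.2) and, for scheduled screening draws, after chemotherapy has started (protocol 7.1.2). The same value is used for the maintenance table (SAP 2.9.3). CR patients enter maintenance with recovered counts (protocol 7.1.4.3 and 7.2.1).

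**Step 2. Follow four possible patients, all at grade 4 at the pre-midostaurin baseline.**

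| Patient | At maintenance entry | Worst in maintenance | SAP table shows | Table from period entry shows |
|---|---|---|---|---|
| A, CR | recovered | grade 4 | 4 to 4, unchanged | worsening to 4 |
| B, CR | recovered | grade 3 | 4 to 3, improved | worsening to 3 |
| C, CRi, platelets | grade 4 | grade 4 | 4 to 4, unchanged | 4 to 4, unchanged |
| D, CRi, platelets | grade 3 | grade 3 | 4 to 3, improved | 3 to 3, unchanged |

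C and D are possible because the CRi definition in protocol 7.2.1 sets no lower limit on the residual cytopenia. In the SAP table A shares a cell with C, and B shares a cell with D. New and persistent cytopenia cannot be told apart.

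**Step 3. What sets the size.** Let M be the number of patients in maintenance, all entering recovered. Let p be the share who reach grade 4 in maintenance and q the share at grade 4 at the pre-midostaurin baseline, with the two independent. Then:

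- new grade 4 cases = M × p
- shown as 4 to 4 = M × p × q
- shown as worsening to 4 = M × p × (1 − q)
- shown as improved from 4 = M × (1 − p) × q

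The documents give none of M, p or q. Purely as an illustration, with M = 100 and p = 10% (10 new cases):

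| q | 4 to 4 | Worsening to 4 | Improved from 4 |
|---|---|---|---|
| 20% | 2 | 8 | 18 |
| 50% | 5 | 5 | 45 |
| 80% | 8 | 2 | 72 |

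For p from 5% to 20%, the count on the diagonal runs from 1 of 5 (q = 20%) to 16 of 20 (q = 80%). The fraction is q whatever p is. From a maintenance-entry baseline, all 10 cases would show as worsening. In every row the total with worst grade 4 remains 10.

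**Step 4. Is the alternative baseline available?** Table 7-1 calls for hematology at CR/CRi assessments and places one such assessment before maintenance C1D1. Protocol 7.2.1 likewise bases entry on marrow and blood evaluation. Chemistry differs: after screening, Table 7-1 has it drawn only to work up a treatment-related event or at the physician's choice.

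**Step 5. Avoid double use.** SAP 2.1.1 starts the maintenance period on the day of the first maintenance dose. A pre-dose count on that day would be both the baseline and a candidate for the worst value unless it is excluded from the latter.

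**The case against.** The strongest reply is that the event is captured elsewhere, and for grade 4 neutropenia that is right. The maintenance hold rule makes it an abnormality that requires a change in study medication, which protocol 8.1.1 and 8.1.2.1 count as an adverse event. SAP 2.9.1 tabulates adverse events by period and maximum severity, counts events with different start dates within each period, and has a separate table for events leading to reduction or interruption. None of this uses the laboratory baseline. The shift table's worst-grade totals also still count every grade 4 value, and SAP 2.9.3 lists all laboratory data with grades.

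A reader might therefore infer too much: that the primary safety result understates marrow toxicity. The documents do not support that. The primary endpoint is made up of adverse-event proportions and deaths (protocol Table 3-1, SAP 1.2), and no shift table enters it.

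Three other extensions also fail. Chemistry should not be re-based, because a pre-period value would often be missing or would have been drawn because of an earlier toxicity. A re-based consolidation table would mainly show cytarabine nadirs. And a grade 4 count in maintenance is not a clean measure of midostaurin's own effect, since there is no control arm and CRi patients may enter with cytopenia.

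What remains is narrower. Protocol 6.3.3.1 has no hold rule for platelets or for grade 3 neutropenia in maintenance. Those counts become adverse events only if they are symptomatic, judged clinically significant, or lead to therapy or a medication change. The shift table should give a grade-based view that does not depend on that judgment, and for change during maintenance it does not.

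**Conclusion.** The point holds for the maintenance neutrophil and platelet shift tables. It follows from the SAP's definitions and needs no numerical assumption: a patient at grade 4 before midostaurin who recovers and falls again to grade 4 appears unchanged, and one who falls to grade 3 appears improved. What is lost is the reading that the cytopenia is new, and only for patients whose baseline was already low. The event itself still counts in the worst-grade totals.

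The size is unknown. Under independence and recovered entry counts, the fraction of new grade 4 cases displayed as unchanged equals the share at grade 4 at baseline, which neither document reports. The illustrative counts show the mechanism and cannot be read as an estimate. The primary endpoint is unaffected. The pre-midostaurin baseline is reasonable for the induction and overall tables: consent follows the start of chemotherapy, so no scheduled on-study count exists before chemotherapy.

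**What to change.** In SAP 2.9.3, for the maintenance neutrophil and platelet shift tables, define baseline as the last non-missing value on or before the first maintenance dose, and state that this value does not count toward the maintenance worst value. Show missing where no pre-maintenance count exists. Keep the pre-midostaurin baseline for the induction and overall tables and for all chemistry tables. A consolidation table from period entry is optional.

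The cost is a short addition to the SAP, one derived variable and a re-run table, with no new data collection. The SAP document history dates the current version after database lock, so the table must be labelled as a post-lock change. No treatment rule is affected.
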